Part III is a three-period, three-sequence crossover study with the primary objective to evaluate the effect of co-administration of soft food on the PK of ABSK061. Part III plans to include 12 healthy participants randomized 1: 1: 1 to Sequence F, Sequence G, or Sequence H to receive a single oral dose of ABSK061 in triplicate doses of Treatment 1, Treatment 2, Treatment 3. Treatment 1 was 5 mg ABSK061 microchip taken with 180 mL of water, Treatment 2 was 5 mg ABSK061 microchip taken with a spoon of yogurt (approximately 15 mL), and Treatment 3 was administered with 5 mg ABSK061 microchip with a spoon of applesauce (approximately 15 mL). Participants in Sequence F will receive Treatment 1, Treatment 2, and Treatment 3 under fasting conditions in the morning on Cycle 1 Day 1 (D1), Cycle 2 Day 1 (D4), and Cycle 3 Day 1 (D7), respectively; participants in Sequence G will receive Treatment 2, Treatment 3, and Treatment 1 in the morning on D1, D4, and D7, respectively; participants in Sequence H will receive Treatment 3, Treatment 1, and Treatment 2 fasted in the morning on D1, D4, and D7, respectively. All participants were required to drink 180 mL of water immediately after swallowing the investigational drug. The washout period for each period was 3 days. The study design is shown in Table 3 Part III Study Design.

Table 3 Part III Study Design

	Cycle 1	Cycle 2	Cycle 3
Sequence F	Treatment 1	Treatment 2	Treatment 3
Sequence G	Treatment 2	Treatment 3	Treatment 1
Sequence H	Treatment 3	Treatment 1	Treatment 2

Note: Treatment 1: 5 mg ABSK061 micro-tablets were administered with 180 mL of water; treatment 2: 5 mg ABSK061 microchip + 1 tablespoon yogurt; treatment 3: 5 mg ABSK061 microchips + 1 tablespoon of applesauce. The washout period of each cycle was 3 days.

Investigati onal Product

ABSK061 capsules were manufactured and provided by the sponsor in two strengths: 0.2 mg/capsule, containing 4 0.05 mg tablets; 5 mg/capsule containing 10 0.5 mg tablets.

Mode of

The 1 mg dose corresponds to 5 capsules of the 0.2 mg strength, the 5 mg dose corresponds to 1 capsule of the 5 mg strength, the 10 mg dose

administra tion

corresponds to 2 capsules of the 5 mg strength, the 20 mg dose corresponds to 4 capsules of the 5 mg strength, and the 35 mg dose corresponds to 7 capsules of the 5 mg strength. The ABSK061 cap was opened prior to dosing and the microt was poured out and swallowed. See Section 7.6 Investigational Product Administration for details.

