2.2 Secondary Objective

- To assess the safety of ABSK061 microchips taken with soft food in healthy adult participants;
- To explore the dose-exposure proportionality of 1 to 35 mg of ABSK061 microchips in healthy adult participants.

3 Study Endpoints

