4.2 Scientific Rationale for Study Design

ABSK061 is planned to be used to explore the treatment of ACH in the pediatric population. The formulation was changed from capsules in ABSK061-101 to microcapsulated microparticles given that the target population for treatment was children 3 to 12 years of age and the therapeutic dose was low. Pharmacokinetic experiments with single gavage doses of 25 mg ABSK061 capsules and ABSK061-NX microt in Beagle dogs showed no significant difference in PK behavior between the two formulations, with mean Cmax and AUC0-inf of 1510 ng/mL, 2490 ng \cdot h/mL (ABSK061 capsules), and 1300 ng/mL, 2460 ng \cdot h/mL (ABSK061-NX microt), respectively. In ABSK061-101, there was a linear relationship between drug exposure and dose over a single dose of 35 mg. The effective dose of ABSK061 for ACH is expected to be below the dose-linear range of this investigational drug, where a dose range of 1 mg to 20 mg may cover the majority of the ACH pediatric population. In order to better understand the drug exposure of ABSK061 at low doses and the pharmacokinetic characteristics of microchips, referring to the Technical Guidelines for Clinical Pharmacokinetic Studies of Chemical Drugs issued by the Center for Drug Evaluation of the National Medical Products Administration in March 2005, Part I of this study plans to conduct single-dose pharmacokinetic studies at three doses of 1 mg, 10 mg and 35 mg, and multiple dose escalation PK studies of 5 mg and 20 mg will be conducted in Part II to further explore the safety and tolerability of the study drug.

Based on the ABSK061-101 study, no Grade ≥ 2 drug-related adverse events were reported in any of the 6 patients in the 5 to 35 mg BID dose groups, and the three dose groups (1, 10, 35 mg) of a single dose of Part I will be conducted in parallel with a 7-day safety

observation.

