6.1 Physical Properties of Investigational Product

The chemical name of this compound (ABSK061-NX) 3- (2,6-dichloro-3,5-dimethoxyphenyl) -1-methyl-7- (1- (2-morpholinethyl) -1H-pyrazol-4-yl) -1,6-naphthyridin-2 (1H) -one is the free base form of ABSK061.

The formulations provided in this study were ABSK061 capsules in the strengths of 0.2 mg/capsule and 5 mg/capsule, the 0.2 mg strength capsule contained 4 ABSK061 micro-tablets containing 0.05 mg active ingredient, and the 5-mg capsule contained 10 ABSK061 micro-tablets containing 0.5 mg active ingredient. Each tablet contains the following inactive pharmaceutical excipients: microcrystalline cellulose, mannitol, croscarmellose sodium, colloidal silicon dioxide, magnesium stearate, film-coating premix (gastric soluble, where the 0.05 mg microt film-coating premix is pink and the 0.5 mg microt film-coating premix is white).

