7.6 Investigational Product Administration

The drug was administered under fasting conditions. All participants were fasted overnight for at least 10 hours before dosing, drinking water was prohibited from 1 hour before dosing to 1 hour after dosing, and no food was allowed for 4 hours after dosing. The investigational product must be swallowed completely and cannot be chewed. When the number of microchips is large, dosing may be divided into multiple doses, but participants must complete swallowing of all microchips at the prescribed dose within 3 minutes.

After removal of the ABSK061 capsules, open the cap and pour out the corresponding number of microt: 5 0.2 mg capsules for 1 mg ABSK061, 10 microt for 5 mg ABSK061, 2 5 mg capsules for 10 mg ABSK061, 4 5 mg capsules for 20 mg ABSK061, and 70 microt for 7 5 mg 35 mg ABSK061.

Part I & II: all participants received the corresponding number of microchips directly with 180 mL of water.

Part III: participants receiving Treatment 1 took 10 0.5 mg tablets directly with 180 mL of water; participants receiving Treatment 2 dispersed 10 0.5 mg tablets on 1 tablespoon of yogurt (approximately 15 mL) and swallowed together, followed by 180 mL of water immediately; participants receiving Treatment 3 sprinkled 10 0.5 mg tablets on 1 tablespoon of applesauce (approximately 15 mL) and swallowed them together, followed by 180 mL of water immediately.

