9.3.5 PK Data Analysis

ABSK061 pharmacokinetic parameters will be calculated and analyzed by a standard noncompartmental model. The PK profile of single or multiple oral doses of ABSK061 microt was assessed based on the primary pharmacokinetic parameters obtained.

Results of PK parameters and summary data will be provided for each participant. Descriptive statistics (arithmetic mean, standard deviation, coefficient of variation, median, minimum, maximum, geometric mean, and geometric coefficient of variation) were calculated for all PK parameters of oral ABSK061 in each treatment group except for tmax, which will be summarized as median, minimum, and maximum. Data listings for all PK parameters will be provided.

Part III assessed the effect of coadministration with soft food on the PK profile of ABSK061. The main PK parameters (Cmax, AUC0- ∞ , AUClast) were log-transformed and statistically analyzed using a linear mixed-effects model. The dosing sequence and period in the model served as fixed effects and participants (in sequence) served as random effects. The magnitude of the difference between the Least Squares Means (and their 90% confidence intervals and the Ratio of the Geometric Least Squares Means (RGLSM, taken with soft food/water) and their 90% confidence intervals were estimated by logarithmic transformation, and the intra-individual coefficient of variation was calculated for each parameter.

In addition, the dose-exposure proportionality of ABSK061 microchips was explored by graphical presentation of different doses by primary PK parameters (Cmax, AUC0- ∞ , AUClast) and/or dose-normalized primary PK parameters for each treatment group. If applicable, the dose-exposure proportionality will be further explored through the Power model by natural log-transformation of the primary PK parameters.

The detailed analysis plan will be further described in the Statistical Analysis Plan (SAP).

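### Does the exploratory 1–35 mg proportionality slope need changing because only the 1 mg dose is made of 0.05 mg micro-tablets?

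*Protocol*

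**What the plan says.** Section 2.2 sets the secondary objective: "To explore the dose-exposure proportionality of 1 to 35 mg of ABSK061 microchips in healthy adult participants". Section 9.3.5 plans graphs of the primary PK parameters and/or "dose-normalized primary PK parameters for each treatment group", and then, if applicable, "the dose-exposure proportionality will be further explored through the Power model by natural log-transformation of the primary PK parameters". It attaches no acceptance limit, does not fix which doses or parts enter the model, and leaves the detail to the SAP.

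On the product, the synopsis (mode of administration) says "The 1 mg dose corresponds to 5 capsules of the 0.2 mg strength", and section 6.1 says "the 0.2 mg strength capsule contained 4 ABSK061 micro-tablets containing 0.05 mg active ingredient". The 5, 10, 20 and 35 mg doses are 1, 2, 4 and 7 capsules of the 5 mg strength, each holding ten 0.5 mg micro-tablets. Section 7.6 agrees: "5 0.2 mg capsules for 1 mg ABSK061, 10 microt for 5 mg ABSK061". No dose is given in both tablet strengths.

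Section 6.1 lists one set of excipients for both tablets. The only difference it states, apart from drug content, is the coat: "where the 0.05 mg microt film-coating premix is pink and the 0.5 mg microt film-coating premix is white".

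**The concern.** A power-model slope over 1–35 mg is naturally read as dose linearity of the drug. Here the lowest dose differs from the others in tablet strength as well as in dose, and on a log scale the lowest dose has the most leverage. If the 0.05 mg tablet released or absorbed differently, the slope would move for a reason unrelated to dose. Dose-normalised plots could show the 1 mg group off the line, but not why.

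The low end also matters to the programme. Section 4.2 gives as a reason for Part I: "In order to better understand the drug exposure of ABSK061 at low doses and the pharmacokinetic characteristics of microchips". Section 4.3 expects 0.1 to 0.5 mg/kg in children with median weights of 12 to 31 kg. At 0.1 mg/kg that is 0.1 × 12 = 1.2 mg to 0.1 × 31 = 3.1 mg, all below 5 mg, where 1 mg is the only dose studied. The protocol gives no exposure comparison of the two strengths; the dog study in section 4.2 compares the earlier capsule with the micro-tablet.

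The obvious remedy is a second slope from the 0.5 mg tablet doses only. The question is whether it would help.

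**Working it through.** **Inputs.** Group sizes are from section 5.1: Part I, 6 each at 1, 10 and 35 mg; Part II, 6 each at 5 and 20 mg; Part III, 12 at 5 mg with water (Treatment 1). Section 9.1 gives intra-individual CVs of 27.272% (AUC0-∞) and 21.966% (Cmax), set at 70% of the between-patient values. The implied between-participant CVs are 27.272/0.7 = 39.0% and 21.966/0.7 = 31.4%. With SD = √ln(1+CV²), the log-scale SDs are 0.376 and 0.306.

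**The plan's own figure.** The protocol states no precision for the slope. Its Part III table does reproduce. For AUC0-∞ at n = 12, the half-width is t(0.95, 20) × √ln(1+0.27272²) × √(2/12) = 1.725 × 0.268 × 0.408 = 0.189, as printed. All nine cells match to three decimals.

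**Effect of a strength difference.** Fit ln(PK) = a + b·ln(dose) by least squares. Let F be the relative bioavailability of the 0.05 mg tablet (assumed). The expected slope moves by w·ln F, with w = Σ over the 1 mg participants of (x − x̄)/Sxx and x = ln(dose). The 90% half-width is t(0.95, n−2) × SD/√Sxx.

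| | Part I, n = 18 | All parts pooled, n = 42 |
|---|---|---|
| Sxx | 39.02 | 47.67 |
| Share of Sxx from 1 mg | 58.6% | 48.1% |
| w | −0.300 | −0.246 |
| 90% half-width, CV 39.0% | 0.105 | 0.092 |
| 90% half-width, CV 31.4% | 0.086 | 0.075 |
| Slope if F = 0.90 | 1.032 | 1.026 |
| Slope if F = 0.80 | 1.067 | 1.055 |
| Slope if F = 1.25 | 0.933 | 0.945 |

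Example: Part I at F = 0.80 gives 1 − 0.300 × ln 0.80 = 1.067. The expected 90% CI at CV 39.0% is 1.067 ± 0.105 = 0.962 to 1.172; pooled it is 1.055 ± 0.092 = 0.963 to 1.147. Both include 1. For F < 1, the expected interval leaves 1 only when F falls below about 0.69–0.71 (CV 39.0%) or 0.74–0.75 (CV 31.4%). At F = 1 the effect is zero.

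**What the same-strength fit would do.** Dropping 1 mg sets w to 0 but leaves only 5–35 mg. In Part I alone that means 10 and 35 mg, n = 12, with half-width 0.314 (CV 39.0%) or 0.256 (CV 31.4%), which is too wide to be useful. The fit must therefore pool parts: n = 36, Sxx = 20.93, half-width 0.139 or 0.113.

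Pooling has its own cost. In that fit 10 and 35 mg come only from Part I, 20 mg only from Part II, and 5 mg only from Parts II and III, and section 7.2 does not randomise between parts. Let g be the ratio of exposure in Part I to that in Parts II and III (assumed, like F). The slope then moves by 0.372 × ln g, because the weights (x − x̄)/Sxx of the 10 and 35 mg participants sum to 0.372. At g = 0.80 the slope is 1 + 0.372 × ln 0.80 = 0.917. With the 1 mg group kept (n = 42), the corresponding weight is −0.001, because the mean of ln(dose) in Part I (1.953) almost equals the overall mean (1.955).

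Adding a term for each part reduces the usable Sxx from 20.93 to 10.47 and widens the half-width to 0.197 (CV 39.0%) or 0.160 (CV 31.4%). Part III has one dose, so it then adds nothing to the slope.

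**The case for a change.** The best argument for acting is that the aliasing is fixed by the assignment of doses to capsule strengths, so no later model can undo it. What can be settled beforehand is how the result will be read. A sentence written before the data would prevent a convenient explanation if the 1 mg group falls off the line, and an unqualified claim of linearity if it does not. The extra fit needs no new samples.

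The first part stands: reading the slope as drug linearity below 5 mg assumes that the two strengths are equivalent, and the protocol does not say so. The case for the extra fit does not. It leaves out the only dose below 5 mg, so it cannot tell a strength effect from low-dose non-linearity. It gives up precision, and it takes on a part effect with a larger weight (0.372) than the strength effect it removes (0.300 or 0.246). Some analysts would still show it as a sensitivity analysis with part terms. That is a reasonable choice, of the kind section 9.3.5 leaves to the SAP.

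**Conclusion.** The observation is correct, but no change to the protocol follows. Tablet strength and the 1 mg dose cannot be separated with this trial's data, and the suggested fit avoids that problem without solving it. Sections 2.2 and 9.3.5 ask about proportionality of the micro-tablet product, and for the product as dosed the 1–35 mg slope is valid. The analysis is secondary, exploratory and conditional, with no pass/fail limit, so no decision in the plan turns on it.

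The size rests on assumed values of F. Between 0.80 and 1.25 the expected slope moves by at most 0.067, inside the 90% half-width of 0.075 to 0.105 for the same data set and CV. The common excipient list makes F near 1 plausible but does not show it. The half-widths also assume that the between-patient CVs implied by section 9.1 carry over to healthy participants, with one fasted-water observation per participant. What is left is a matter for the study report: state that conclusions below 5 mg assume the two strengths are equivalent, and cite comparability data if the sponsor holds them.

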9.3.6 Safety Analysis

Adverse events, clinical laboratory data, vital signs, and electrocardiograms will be assessed using the Safety Analysis Set, with descriptive statistical analysis as the main. Missing safety data will not generally be imputed unless otherwise specified.

9.3.7 Adverse Events

Adverse events occurring in each participant were coded by system organ class and MedDRA preferred term in the Medical Dictionary for Regulatory Activities (MedDRA). The incidence of treatment-emergent AEs, TEAEs (new or pre-dose but worsening after the first dose to the last safety follow-up visit) will be summarized. All adverse events, study drug-related adverse events, serious adverse events (SAEs), and adverse events leading to death will be listed.

9.3.8 Laboratory abnormalities

Laboratory measurements and changes from baseline will be summarized descriptively

(mean, median, standard deviation, maximum, minimum) by treatment group. Listings with abnormal values will be provided.

The results of hematology, blood chemistry, urinalysis, and clinical significance as judged by the investigator included in the CRF will be summarized according to the scheduled visit. The number and percentage of participants with measurements judged high, low, or normal compared to the normal laboratory range will be summarized by treatment group using a crossover table, if applicable.

9.3.9 Other safety data

Data from other tests (e.g., electrocardiograms or vital signs) will be listed and flagged with abnormal values. Summary tables of additional safety data will also be provided.

9.3.10 Interim Analysis

Not applicable for this study.

10 Study Management

10.1 **Good Clinical Practice**

This study will be conducted in strict compliance with the regulatory requirements of ICH-GCP. The investigator needs to be fully familiar with the protocol and the rational use of the investigational product. Necessary clinical documents will be retained to demonstrate compliance with the study and the reliability of the data. Study main body documents should be established at the start of the study and maintained throughout the study as required by regulations.

10.2 Ethical norms

The study will strictly follow the ethical principles of the Declaration of Helsinki. The IRB/IEC/REB will review all study documents to safeguard the rights, safety and welfare of participants. The study will be conducted only at sites approved by the IRB/IEC/REB. Amendments to the protocol, informed consent form, written information given to participants (including diary cards), and other documents will be submitted by the investigator to the IRB/IEC/REB.

10.3 **Informed Consent**

Participants should fully understand the contents of the study and sign the informed consent form before participating in this study. The method of obtaining and documenting informed consent and its contents will comply with the requirements of ICH-GCP and all applicable regulations.

10.4 Clinical Monitoring

Shanghai Hezhui Biopharmaceutical Technology Co., Ltd. will conduct inspections and reviews during the study to ensure that the study complies with GCP guidelines. Monitoring activities will be conducted by Shanghai Hezhui Biopharmaceutical Technology Co., Ltd., or designated third party designated monitors, including on-site review of eCRF integrity and clarity, cross-validation with source documents, reconciliation of other matters required by regulatory requirements, etc. The review of medical records will be conducted in a manner that ensures participant privacy.

The monitor will ensure that the investigator complies with the protocol design and regulatory requirements by frequent correspondence (letter, telephone, fax). Regulatory authorities, IRBs/IECs/REBs, and/or sponsors (or designated third parties) have access to all source documents, CRFs, and other study documents at the time of on-site verification. Sponsors need to ensure that these documents are readily accessible to support these activities.

10.5 Protocol Amendment

The investigator will conduct the clinical study in accordance with the protocol provided by Shanghai Hezhui Biopharmaceutical Technology Co., Ltd. The protocol will be approved by the IRB/IEC/REB and the corresponding regulatory authorities. The protocol contents may not be modified without the consent of the sponsor and the investigator. Protocol amendments need to be approved by the IRB/IEC/REB, unless they directly threaten the rights and interests of participants. Shanghai Hezhui Biopharmaceutical Technology Co., Ltd. will ensure compliance with regulatory requirements and submit all protocol amendments to regulatory authorities. Substantial amendments to the protocol can be made only after approval by regulatory authorities and the IRB/IEC/REB. When protocol deviations that pose a direct hazard to participants need to be immediately eliminated, the investigator should contact Shanghai Hezhui Biopharmaceutical Technology Co., Ltd. as circumstances permit to discuss the action plan. All deviations from the protocol need to be fully documented.

10.6 **Data Quality Control**

To ensure the accuracy, completeness and reliability of the data, Shanghai Hezhui Biopharmaceutical Technology Co., Ltd. or its designated third party will perform the following:

- Provide guidance materials to sites as needed;
- Provide training as needed to guide investigators and clinical coordinators. Specific training content will involve the protocol, CRFs and study procedures;
 - Regular visits to the study site;
 - Maintain contact with site staff by mail, telephone, and/or fax;
- Review and assess CRF data and/or use standard computer editing to detect errors in data collection;
 - Perform a quality review of the database.

In addition, Shanghai Hezhui Biopharmaceutical Technology Co., Ltd. or its representatives will be inspected based on participant data samples recorded in the site source documents. Shanghai Hezhui Biopharmaceutical Technology Co., Ltd. and/or regulatory authorities may review the study at any time.

10.7 **Data Collection Tools/Source Data**

The CRF Data for this study will be completed using an Electronic Data Capture (EDC) system, and all source records will be defined and retained by the site, and all records of source Data entered into the EDC system will be retained.

10.8 **Participant Confidentiality Measures**

To maintain participant privacy, all CRFs, investigational product records, study reports,

and correspondence will identify participants by designated participant numbers. The study personnel will grant monitors and inspectors access to the participant 's original medical records to Shanghai Hezhui Biopharmaceutical Technology Co., Ltd. or its designees and regulatory authorities to verify the data collected on the CRFs and review the data collection process. To the extent permitted by applicable laws and regulations, the privacy of participants will be strictly protected from disclosure.

10.9 **Record Retention**

The investigator will retain all study records as required by ICH-GCP and other applicable regulations. If the investigator is no longer responsible for the retention of study records, regulatory authority needs to be transferred to other persons willing to assume responsibility. Shanghai He Gloria Biopharmaceutical Technology Co., Ltd. shall be notified in writing of any change in custody.

